Methodology	To achieve all of our research objectives, we plan to conduct a two-arm RCT pilot study of a CDS intervention, exposing half of our clinician sample to the TUT Service+VM condition during clinical workflow, and comparing important outcome measures to those observed among the half exposed to the current usual care condition, TUT Service alone.
Study Duration	The study will take place over a period of 2 years.
Study Center(s)	The Penn Presbyterian Medical Center (PPMC) at the University of Pennsylvania will serve as the primary project location, and all recruitment and data collection efforts will be executed by University of Pennsylvania staff members.
Objectives	
Specific Aim 1: Assess whether including a standing order for prescription and management of varenicline (TUT Service+VM) within the workflow for patients (cancer or non-cancer) identified as current smokers will significantly increase TUT engagement rates compared to current standard of care (TUT Service alone).
 
Specific Aim 2: Assess whether clinicians exposed to the TUT Service+VM condition will be more effective at guiding reluctant patients toward TUT engagement than clinicians exposed to the TUT Service alone condition.
 
Specific Aim 3: Assess implementation preferences and barriers influencing effectiveness of usual care tobacco use treatment (TUT Service) + varenicline management (VM) applied within the cancer center.

Number of Subjects	Recruitment will include projected subject recruitment totals of 52 PPMC clinicians.

Main Inclusion and Exclusion Criteria	
Subject Inclusion Criteria:
 
• Provides care for inpatients with a cancer diagnosis at PPMC as a hospitalist or attending in the Department of Medicine• Prescribing authority in Pennsylvania (i.e. physician, nurse practitioner, physician assistant);• Has cared for at least one patient with tobacco use disorder in the 30 days prior to recruitment;• English speaking
Intervention	Our research objective is to identify a simple, pragmatic, innovative way of enhancing TUT rates within medical care, including oncology. To investigate this possibility, we propose methods that will allow us to: 1) evaluate the impact of standing orders to initiate a varenicline management protocol within inpatient cancer and non-cancer treatment workflow and 2) assess the potential for an EHR-based intervention to affect patient TUT behaviors.
Statistical Methodology	
For Aims 1 and 2, rate comparisons between the two groups will be performed using Chi-square.
 
For Aim 3, average scores will be calculated for ratings of barriers and facilitators to effectiveness of implementing VM,

Data and Safety Monitoring Plan	The study will be monitored by the PIs and co-investigators, and regulatory committees at the University of Pennsylvania (i.e., IRBs, OHR). During the course of the study, safety and data quality monitoring will be performed on an ongoing basis by the Principal Investigator and the study staff.

1 Introduction

To reduce all-cause and cancer-specific mortality, the 2014 Surgeon General's Report emphasized the importance of effective tobacco use treatment (TUT) in within medical care, including cancer care.(1) Unfortunately, up to 50% of cancer patients who smoke prior to their diagnosis continue to do so after diagnosis and treatment.(2) This observation has lead the National Comprehensive Cancer Network,(3) the American Society of Clinical Oncology,(4) and the American Association for Cancer Research(5) to call for implementation strategies integrating TUT directly within oncology care. At this time, many cancer centers and oncology practices, and general inpatient medical facilities, fall short of providing consistent, high-quality TUT; only half of cancer centers report that they identify tobacco use among patients,(6) and very few use systematic mechanisms to encourage TUT services.(5)

In response, the National Cancer Institute (NCI) funded the Cancer Center Cessation Initiative (C3I) in 2017 with support from the NCI Cancer Moonshot Program.(7) C3I's aim is to help build and sustain TUT infrastructure across the nation's cancer centers, ensuring that cancer patients are systematically screened for tobacco use and provided with evidence-based smoking cessation treatment.(8) Abramson Cancer Center's work implementing the C3I tobacco use treatment service (TUT Service) has

significantly improved rates of TUT within oncology practice, however we have identified a number of important social-motivational obstacles to reaching our target of universal TUT. For instance, we know that simple changes to treatment choice architecture in the electronic health record (EHR), i.e. utilizing an “opt-out” rather than “opt-in” structure, increases TUT Service engagement in a manner similar to other contexts of cancer care.(9) Unfortunately, there remains unacceptable variation in clinician engagement rates. One significant reason for this variation is the individual clinician’s perceptions of treatment effectiveness.(10–12) A strategy used elsewhere involved utilizing opt-out orders aimed at maximizing the use of varenicline, i.e. “Varenicline Management” (VM). VM resulted in increased clinician utilization and patient cessation within a relatively controlled environment of hospital-based cardiac and pulmonary care.(13,14) However, it is unknown whether this type of intervention is generalizable to the complex, challenging environment of inpatient oncology.

Our research objective is to identify a simple, pragmatic, innovative way of enhancing TUT rates within inpatient medical care and, specifically, for oncology inpatients. To investigate this possibility, we propose methods that will allow us to: 1) evaluate the impact of standing orders to initiate a varenicline management protocol within inpatient medical treatment workflow (that will include cancer and non-cancer patients) and 2) assess the potential for an EHR-based intervention to affect patient TUT behaviors.

1.1 Study Significance and Rationale

Insights from prior work: Our group has been engaged in efforts to understand the behavioral economic landscape informing clinician choice for several years. In a discrete choice analysis of alternatives determining physicians’ preferences for generic “smoking cessation strategies,” effectiveness of the intervention was a statistically significant determinant of preference, with a relative utility 100-fold greater than either reimbursement rate or time saving capacity. This observation led us to examine the role of several cognitive biases in influencing physicians’ perceptions of success probabilities under conditions of uncertainty.(11) Educational efforts that minimize availability bias, omission bias, impact bias and focusing effect bias more successfully change physician TUT behaviors than interventions aimed solely at increasing knowledge.(33) Our group also identified implicit associations between smoking status and a culpability theme, influencing both the emotional characteristics of physician-smoker interactions and willingness to invest effort in TUT.(34) It is clear that complex and overlapping social motivators play a significant, perhaps unrecognized, role in physician decision-making around TUT.

Finding solutions: Addressing a variety of complex motivations, within a diverse group of clinicians from multiple disciplines, with widely divergent perceptions about and experience with TUT, will require an approach that moves beyond traditional behavior change communications (BCC), and integrates several different theory-based behavioral economic (BE) interventions within a cohesive theme (Fig 1).(35) Our project represents an innovative approach to incorporating several BE insights into a simple, practical, system change that has the potential to meet a variety of needs. At baseline, our CDS facilitates identification of smoking status, and relies on harnessing social norms to encourage physicians to opt-in. Our varenicline management (VM) intervention (described in full below) adds several BE dimensions to the CDS, namely: 1) removal of obstacles to decision-making

[figure not shown]

Figure 1: Continuum of interventions ranging from Behavior Change Communications to Behavioral Economic influences on choice.

at the moment of treatment planning and order entry, 2) optimization of timing of information-giving by moving medication management to outside the cancer care visit, 3) simplifying treatment decisions by focusing the palette of pharmacotherapies to the one generally recognized as most effective (36), 4) using an opt-out choice architecture to take advantage of defaults, 5) maximizing clinician perceptions of effectiveness by presenting relative efficacy data directly within the order field, and 6) acting as a very strong commitment device, encouraging both clinicians and patients to engage in important follow-up activities.

Why varenicline: The initial 2006 reports of varenicline's impact on tobacco dependence suggested superior efficacy to other available pharmacotherapies, including nicotine replacement and bupropion.(36,37) Since then, varenicline has been generally well accepted as first-line therapy in a general population of smokers, with an abstinence odds ratio (OR) of ~2 when compared to other pharmacotherapies.(38) Cancer patients are *not* more likely to spontaneously quit because of their illness (39), however studies have confirmed varenicline's similar efficacy in cancer patients who continue to smoke.(40) Initial concerns over the possible neuropsychiatric side-effects of varenicline appear to have been overblown(41), with the most recent and comprehensive data suggesting efficacy, safety, and tolerability, even in patients with pre-existing depression and psychiatric disease.(42) Perhaps most encouraging is the observation that varenicline is effective in promoting cessation even in patients unwilling to make a quit attempt at the time of treatment initiation, making it the ideal candidate for a CDS intervention designed to produce minimal interruption to oncology treatment workflow.(43–45)

2 Study Objectives

The multi-disciplinary team assembled for this study implemented the ACC TUTS program. Drs. [name] and [name] oversee this program. This is a pragmatic study. The specific aims are described below.

2.1 Primary Objectives

The objective of this study is to examine a novel approach to improving the quality of care inpatients receive if they use tobacco (oncology and general inpatients).

Specific Aim 1: *Assess whether including a standing order for prescription and management of varenicline (TUT Service+VM) within the inpatient clinical workflow for cancer and non-cancer patients identified as current smokers will significantly increase TUT engagement rates compared to current standard of care (TUT Service alone). Hypothesis:* Observed treatment engagement rates will be higher among clinicians exposed to TUT Service+VM than observed in clinicians exposed to TUT Service alone.

Specific Aim 2: *Assess whether clinicians exposed to the TUT Service+VM condition will be more effective at guiding reluctant patients toward TUT engagement than clinicians exposed to the TUT Service alone condition. Hypothesis:* Rates of important TUT behaviors (e.g. treatment initiation, quit attempts, and others) observed among smoking patients of clinicians exposed to TUT Service+VM will be higher than those than observed among smoking patients of clinicians exposed to TUT Service alone.

Specific Aim 3: *Assess implementation preferences and barriers influencing effectiveness of usual care tobacco use treatment (TUT Service) + varenicline management (VM) applied within the cancer center. Hypothesis:* Oncology specialists exposed to the TUT Service + VM condition will identify key facilitators and barriers to the implementation of the TUT Service + VM condition that can help guide subsequent dissemination efforts.

The goal of this study is to determine if the default for a varenicline order increases clinician referral to TUTS and/or the treatment of tobacco use. At this point, many clinicians are turning the referral order off and patients are not receiving treatment for tobacco use. A default to prescribe treatment may help override barriers to both. While we are focused on cancer inpatients, we will assess the impact of the varenicline management intervention on cancer and non-cancer patients.

Insights gained from this project form the basis of subsequent clinical trials assessing efficacy of novel implementation approaches improving uptake of evidence-based tobacco use treatment within the inpatient clinical setting. This study is significant because the model for promoting physician behavior change is simple and pragmatic yet has the potential to significantly impact patient survival and morbidity. The study builds on previous observations made through NCI and C.U.R.E. investments, expanding our understanding of novel pharmacologic approaches to tobacco cessation.

3 Study Population and Duration of Participation

The study will be conducted within PPMC in the University of Pennsylvania Health System (UPHS). Participants will be hospitalist and attendings in the Department of Medicine who provide care for inpatients with a cancer diagnosis at PPMC. This study will recruit individuals age 18 or older only. Children under age 18 will not be eligible for this trial.

We plan to derive a sample of 52 clinicians from the available pool of several hundred eligible PPMC clinicians.

No data are to be collected from the patients aside from routinely collected patient-level data regarding tobacco treatment use once patients are referred to [name] tobacco treatment program; patient data are available in the EHR. If clinicians place the referral order (which is already in EPIC) to [name] smoking cessation service, we collect standard information concerning smoking behavior that is standard clinical information, not research data (e.g., use of smoking cessation treatments, quit attempts). No patient data will be collected outside of what is available in the EHR (for clinicians in the study) or what is collected clinically when patients contact the cessation program from the clinician's referral. All patients receiving care from eligible clinicians will be assessed in this study as described above, those with or without cancer, so that we can test the impact of the intervention for cancer inpatients as well as for those inpatients without a cancer history.

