4.2 Study Measures

Our current usual care CDS “fires” a Best Practice Alert (BPA) for each new inpatient within the Medical Assistant (MA) check-in and vital sign workflow. The BPA requires that MAs assess tobacco use status within the past 30 days and satisfy the alert with one of three possible, mutually exclusive answers.

Intervention ordering rate is defined as the number of patients for whom any inpatient tobacco use treatment order (for medication, education, and/or TUTS counseling) was signed divided by the total number of patients in each arm for whom an order was pended and the alert fired. MAs activate “Order” tab for all patients identified as current smokers (within 30 days), resulting in placement of pended order for consult to TUT Service referral within clinical workflow.

Inpatient medication ordering rate is defined as the number of patients for whom a tobacco use treatment medication was ordered in the inpatient setting divided by the total number of patients in each arm for whom an order was pended and the alert fired.

Outpatient/discharge medication ordering rate is defined as the number of patients for whom a tobacco use treatment medication was ordered upon patient discharge from the hospital divided by the total number of patients in each arm for whom an order was pended and the alert fired.

TUTS referral rate is defined as the number of patients for whom a referral to Penn Medicine’s Smoking Cessation Program was placed in the inpatient setting divided by the total number of patients in each arm for whom an order was pended and the alert fired.

These measures will be collected only from patients referred to [name] program for treatment:

Quit Line rate, defined as the total number of patients who present for quit line counseling (i.e. telephone or electronic), divided by the total number of patients referred to the Smoking Cessation Program

Medication recommendation rate, defined as the total number of patients who are recommended to receive a tobacco use treatment medication by the TUT Service staff in quit line counseling divided by the total number of patients who present for quit line counseling

Follow-up recommendation rate, defined as the total number of patients who are recommended to receive a tobacco use treatment medication or a follow-up appointment by the TUT Service staff in quit line counseling divided by the total number of patients who present for quit line counseling

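### Section 4.2 gives Aim 2 no measure of quit attempts, medication start or reluctance, and its downstream rates are conditional on a referral that the intervention is meant to change

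*Combined protocol and SAP*

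**What the plan says.** Section 2.1 asks in Aim 2 whether clinicians in the TUT Service+VM arm will be "more effective at guiding reluctant patients toward TUT engagement than clinicians exposed to the TUT Service alone condition". The hypothesis is that "Rates of important TUT behaviors (e.g. treatment initiation, quit attempts, and others) observed among smoking patients of clinicians" will be higher in that arm.

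Section 4.2 defines seven rates and assigns none of them to an aim. Four are divided by the patients in the arm with a pended order and a fired alert: any treatment order, inpatient medication order, discharge medication order and TUTS referral. The other three are introduced by "These measures will be collected only from patients referred to" the treatment program:

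- Quit Line rate: the "total number of patients who present for quit line counseling (i.e. telephone or electronic"), divided by patients referred.
- Medication recommendation rate: patients "recommended to receive a tobacco use treatment medication by the TUT Service staff in quit line counseling", divided by presenters.
- Follow-up recommendation rate: patients "recommended to receive a tobacco use treatment medication or a follow-up appointment by the TUT Service staff", divided by presenters.

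Section 3 states that, once a referral is placed, "we collect standard information concerning smoking behavior that is standard clinical information, not research data (e.g., use of smoking cessation treatments, quit attempts"). Section 5.5 says that Aim 2 rests on self-report at in-person contact with tobacco treatment specialists. Section 6.2 applies a chi-square test to unnamed rates for Aims 1 and 2, and looks at cancer, non-cancer and all inpatients. Section 8.2 says that the only information collected for research comes from the qualitative interview.

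**The concern.** There are two gaps. First, the behaviours and the population named in Aim 2 are not turned into outcomes. Quit attempts and medication start have no numerator, denominator or time point, and nothing identifies a reluctant patient. Second, the downstream rates that are defined apply only to patients selected after randomization. Referral is the step that the intervention is designed to change, so the referred patients in the two arms need not be alike.

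If the plan is followed as written, the Aim 2 test could be run on a ratio whose denominator moves with treatment. A real gain in patients reaching counselling could then appear as a loss. With the outcomes left open, the choice of which patient behaviours to report could also be made after the data are seen.

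**Working it through.** **Step 1. Aim 2 terms against the seven rates in section 4.2**

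| Term in Aim 2 | Matching rate | Count |
|---|---|---|
| Quit attempts | none | 0 of 7 |
| Medication start | none; the medication rates count orders or staff recommendations | 0 of 7 |
| Start of counselling | Quit Line rate, per referred patient | 1 of 7, partial |
| Reluctant patients | none; no definition, and no such subgroup in 6.2 | 0 of 7 |

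**Step 2. The planned referral rates.** Section 6.1 gives about 600 referrals from 1,000 alert activations: 600 / 1,000 = 60%, which reproduces the stated engagement rate. The target is 80%. Per 100 alerts, the plan therefore expects 60 referrals in control and 80 in the intervention arm, 20 of them extra. The clinician sample size in 6.1 concerns the engagement rate and plays no part here.

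**Step 3. What the Quit Line rate does when referral rises.** Let r0 = 0.60 and r1 = 0.80. Let u0 be the share presenting among patients who would be referred in either arm, and u1 the share among the extra referrals. The documents give neither u0 nor u1, so both are assumptions. The intervention is assumed not to change u0.

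- Control: presenters per alert = r0 × u0; Quit Line rate = u0.
- Intervention: presenters per alert = r0 × u0 + (r1 − r0) × u1; Quit Line rate = that quantity / r1.

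With u0 = 50% and u1 = 10%, presenters per alert in the intervention arm are 0.60 × 0.50 + 0.20 × 0.10 = 0.32, and the Quit Line rate is 0.32 / 0.80 = 40%.

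| u0 | u1 | Quit Line rate, control | Quit Line rate, intervention | Per alert, control | Per alert, intervention |
|---|---|---|---|---|---|
| 50% | 0% | 50% | 37.5% | 30% | 30% |
| 50% | 10% | 50% | 40% | 30% | 32% |
| 50% | 50% | 50% | 50% | 30% | 40% |
| 50% | 60% | 50% | 52.5% | 30% | 42% |
| 30% | 10% | 30% | 25% | 18% | 20% |

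Under these assumptions the intervention Quit Line rate is below control exactly when u1 < u0, and presenters per alert are higher whenever u1 > 0. For any u1 between 0 and u0 the two measures point in opposite directions.

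**Step 4. The recommendation rates.** Their denominator is selected twice, by referral and then by presentation, and their numerator is an action of TUT Service staff. Section 5.2 also routes intervention patients to TUT Service prescribers with a varenicline prescription already pended, so a medication recommendation may partly reflect the arm's own procedure.

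**Step 5. Why quit attempts cannot simply be divided by alerts.** Suppose 30% of patients in both arms truly attempt to quit (an assumption), that all attempts are recorded in referred patients and that unreferred patients are coded as no attempt. The recorded rates are 0.60 × 30% = 18% in control and 0.80 × 30% = 24% in the intervention arm. That is a difference of 6 percentage points with no true effect.

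**The case against.** The strongest reply is that the plan is less empty than it looks. The hypothesis list is open-ended. The Quit Line rate is a patient behaviour and partly captures the start of counselling. The two medication-order rates bear on initiation and already use all alerted patients. Sections 3 and 5.5 show that treatment use and quit attempts are recorded clinically and that self-report is meant to serve Aim 2. The hypothesis itself compares smoking patients; reluctance appears only in the lead sentence of the aim. The trial is a pilot sized on engagement, so its main conclusion does not depend on Aim 2.

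Most of this stands, and it limits the point. A reader might infer that no listed measure touches any Aim 2 behaviour, or that the data do not exist. The Quit Line rate contradicts the first and section 3 the second. What is missing is outcome definitions and a randomized comparison.

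A reader might also infer that the roughly 40% of control alerts without a referral are the reluctant patients, or that referred patients are the least reluctant. The documents do not support either. Referral is a clinician's order, and section 2.1 attributes missing referrals to clinicians turning the order off. The 40% is one minus the engagement rate and measures neither reluctance nor bias.

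The reply does not cure the gap. An open list defines nothing, an order is not a patient starting treatment, and the denominators remain conditional on referral.

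**Conclusion.** The point holds for quit attempts, medication start and reluctance, none of which has a defined measure, and for the three downstream rates, which do not compare the groups as randomized. The possible distortion is material. At the planned 60% and 80% referral, with 50% uptake among patients who would be referred in either arm, the intervention Quit Line rate runs from 37.5% to 52.5% against 50% in control as uptake among the extra referrals runs from 0% to 60%. Presenters per alert run from 30% to 42% against 30%. Those uptakes are assumed, so the figures show that the direction can reverse, not that it will. The result also assumes that the intervention leaves uptake unchanged among patients who would be referred anyway, and that alert firing does not depend on arm.

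This should be changed before analysis. It does not touch the engagement comparison, which section 6.1 names as the primary measure of effect.

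**What to change.** In section 4.2:

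1. Make treatment initiation the between-arm outcome for Aim 2: presentation for counselling, or a recorded start of a cessation medication where the EHR captures it regardless of referral. Give a time point, and state whether the call-back that section 5.2 describes for the intervention arm counts as presentation.
2. Use as denominator all patients for whom an order was pended and the alert fired. Count patients who never present, and have no recorded medication start, as not initiating.
3. Keep the per-referred and per-presenter rates as descriptive only, and report by arm the share of patients with any TUT contact.
4. Report recorded quit attempts descriptively among patients with TUT contact, with no between-arm test. Do not code unreferred patients as having made no attempt, because ascertainment differs by arm.

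In section 2.1, restate the Aim 2 population as smoking patients with an alert and drop *reluctant*. In section 6.2, name the Aim 2 outcome that is tested. Reconcile sections 3 and 8.2 with the research use of these clinical data.

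The cost is protocol and SAP wording and a minor extra analysis of data already collected. The price is a narrower claim: Aim 2 would speak to initiation per alerted patient, and not to quit behaviour or to reluctant patients.
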